**Figure 4. Web-based questions to determine pedometers compliance.**

**Pedometer compliance tracking:** We will utilize RED Cap™, a secure online research database to: 1) track and monitor participant compliance wearing pedometers; and 2) record Non-Ex PA at run-in and during the intervention. Participants will be provided a unique name/password to log on to the study website. The use of RED Cap™ will allow our staff to monitor participant compliance throughout the trial in real-time. Our research team is successfully using RED Cap™ in two on-going prospective physical activity trials.

**3.7 Clinical Visits (baseline, mid-intervention, and follow-up):** We will obtain primary (waist circumference) and secondary outcome measures (DEXA, fitness, blood measures) at both baseline and follow-up (summarized in Figure 5). Pre-menopausal women will be asked to take a pregnancy test. A physician or a physician’s assistant will obtain a medical history and perform a brief medical exam. **All clinic staff measuring outcome measures will blinded to participant randomization.**

At mid-intervention (week 12), we will measure waist circumference, weight, FFQ, and accelerometry. The CON group will be scheduled for mid-intervention and follow-up visits, and will be instructed not to alter physical activity habits during the intervention. All groups will be instructed not to alter dietary habits during the study.

### **3.8 Exercise Training**

**Intervention:** Participants

Phone-screen	Orientation and Run-in	Clinic Evaluation (baseline, mid-intervention and follow-up)

Screen for inclusion/exclusion criteria:
 
 
• Age (40-65 yrs)
 
• BMI (30-40)
 
• Diabetes (No)
 
• Heart disease (No)
 
• Stroke (No)
 
• Currently exercising (No)
 
• Height/weight
 
• Other information: 
 
• Ethnic identification
 
• Contact information
 
• Medication list
 
 
 
	
Orientation:
 
 
• Information session about study
 
• Obtain informed consent for screening and run-in visits
 
 
Run-in:
 
 
• 6 run sessions over 2 weeks to test participants ability to come to PBRC 3 times per week
 
• Informed consent for baseline evaluation
 
• Verify inclusion criteria (ie: baseline physical activity, waist circumference, blood pressure).
 
• Log compliance wearing pedometers using the RED CAP™ system
 
• Blood draw:
 
• Lipids, CBC, chemistry panel, insulin
 
• Intervention interview
 
	
 
• Clinic Evaluation
 
• Physical/review of medical history
 
• Blood pressure
 
• Anthropometry
 
• DEXA
 
• Treadmill exercise test
 
• FFQ
 
 
At baseline: Informed consent for randomization Randomize to the CON, AERO, or AERO-PA group
 
Mid-intervention: FFQ, weight and waist circumference, accelerometry
 
At follow-up: Exit interview

**Figure 5. Study Flow**

will participate in structured aerobic training 3 times a week at a heart rate associated with 50-

75% of  $\text{VO}_{2\text{peak}}$ . All exercise training will occur on a treadmill (or a stationary bicycle only when necessary). Participants will wear heart rate monitors during exercise sessions. The speed and grade of the treadmill will be adjusted in order to keep participants within their heart rate range. Using standard ACSM equations , and adjust the length of each exercise session to meet the daily caloric goal based on the speed, grade of the treadmill, and participants' weight . The caloric goal of each session will be calculated by dividing the weekly caloric expenditure goal by the participant's exercise frequency (i.e. 3 times per week). **Study staff will confirm that pedometers measuring Non-Ex PA are removed prior to beginning aerobic training sessions.** Since individuals in both groups will participate in aerobic exercise training in the same room, they will be reminded frequently not to discuss group assignment with each other.

**Exercise training dose and progression:** Exercise dose (expressed in KKW: kilocalories per kg per week) during aerobic training will be the same in both the AERO and AERO-PA groups. During the first month of the study, both groups will participate solely in structured aerobic training with no intervention on Non-Ex PA (to allow acclimation to aerobic training). Participants in both exercise groups (AERO, AERO-PA) will expend 8KKW in week 1, 10KKW in week 2 and 12 KKW in week 3. We have selected 12 KKW as the selected energy expenditure for aerobic training because, based on our calculations, it most closely represents the current recommendations of 150 minutes per week of moderate physical activity . We have utilized the 12KKW dose successfully in two completed exercise training trials . Thus, the amount of exercise training should be reasonable for participants to perform. For example, at a speed of 3.2 MPH and 2.5% grade, the estimated session time would be approximately 50 minutes for a participant exercising 3 days per week.

**3.9 Non EX-PA:** Our research team has monitored Non-Ex PA successfully in several previous exercise studies. For the AERO-PA group, we will average the amount of Non-Ex PA from week 4 to week 6 (when participants are at the full prescription for exercise training [12KKW]) to determine **the baseline level of Non-Ex PA with exercise training (Figure 6)**. At week 6 of intervention, the AERO-PA group will begin to incrementally increase their Non-Ex PA by an average of 1,000 steps/day above baseline for the first two weeks. Participants will continue to increase Non-Ex PA by at least an average of 500 steps/day every 2 weeks until they reach an average of 3,000 steps/day above baseline (week 14) for the remainder of the intervention. We have selected 3,000 steps as the maximum goal for Non-Ex PA based on data evaluating the increase in steps from pedometry-based interventions with similar study populations/design. These studies suggest that an increase of 2,000-4,000 steps/day is feasible . We elected to utilize a progressive increase in Non-Ex PA to allow participants adequate time to determine behavioral strategies to reach Non-Ex PA goals, and to become acclimated to the higher amounts of total physical activity. The investigative team will not impose any restrictions on how this increase in Non-Ex PA is achieved, with the exception that it is not performed specifically as additional aerobic

[figure not shown]

Figure 6. Non-Ex PA in the AERO and AERO-PA group in a participant walking 4,500 steps/day at baseline

exercise training (i.e. treadmill for 30 minutes). Moderate physical activity consistent with daily living (i.e. leisurely walking in the evening, walking the dog etc.) will be permitted. Participants will be instructed to take a “recuperation day” once every week, where Non-Ex PA will be tracked, but not intervened on for the purposes of the study. We believe that a weekly recuperation day will lessen the total participant burden, and allow adequate recovery time.

**Lifestyle counseling to increase Non-Ex PA in AERO-PA group:** The AERO-PA group will receive lifestyle counseling to help them obtain the required amount of Non-Ex PA. Participants will meet with study staff (~15 mins) once a week (from week 6-10), and every two weeks thereafter. Specific strategies to increase Non-Ex PA will be tailored to each participant (occupational strategies, home strategies, etc.). Lifestyle counseling for the AERO-PA group will occur before or after exercise training sessions, and all sessions will be conducted in a private room to avoid potential contamination with the AERO group. Examples of strategies to increase Non-Ex PA include walking around the house during commercial breaks while watching television, talking on a cell phone while walking instead of sitting, parking car farther away from workplace. The intervention is grounded in the principles of social learning and behavior change theories. Counselors will utilize motivational interviewing and enhancement for participants whose motivation decreases during the study. Behavioral strategies to foster adherence to Non-Ex PA goals include stimulus control, behavioral contracting, problem solving training, and selective reinforcement of target behaviors.

**Plan for Tracking and Monitoring Non Ex-PA:** Similar to run-in visits, during the intervention, we will utilize the study website (RED Cap™ database) to monitor compliance. The AERO group will monitor Non-Ex PA in the same manner as during the run-in period throughout the intervention. In the AERO-PA group only, we will obtain self-reported steps data as a cognitive behavioral tool as well to monitor Non-Ex PA in real-time by study staff. From week 6 to the end of intervention, the AERO-PA group will input the amount of steps completed at the conclusion of the day (or within at least 72 hours of completion), whether they wore their pedometer as instructed, whether this day was a recuperation day, and any comments about Non-Ex PA (Figure 7). Non-Ex PA compliance will be defined as the amount of total days wearing the pedometer versus total amount of days in the study intervention. Adherence will be defined as total amount of steps obtained versus total amount of steps prescribed. **Non-Ex PA values will also be downloaded directly from pedometers in order to obtain objective measures of steps/day in all participants.**

**Control (CON) Group:** As stated earlier, participants randomized to the CON group will be instructed not to change their physical activity habits during the study, but will participate in all assessment visits (i.e. mid-intervention, following-up testing). Non-Ex PA will also be measured in the CON group as participants will wear pedometers during the 6 month intervention in “blind mode” and enter information into the RED Cap™ database online (in the same manner as screening). In addition, participants will come in once a month to Pennington to confirm no changes in sedentary status, download pedometer data (Lifecorder Plus has a 60 day memory), and address any issues with participant compliance.

Intervention (week 6-week 24)
 
AERO Group:
 
Information collected:
 

• Did you wear the pedometer today (yes/No)

• Were there any periods of time where pedometer was not worn (Yes/No)

• If so, please provide an estimate of the approximate time: _____

• Further comments: _____

 
AERO-PA Group:
 
Information collected:
 

• Total amount of steps

• Recuperation day (Yes/No)

• Did you wear the pedometer today (yes/No)

• Were there any periods of time where pedometer was not worn (Yes/No)

• If so, please provide an estimate of the approximate time: _____

• Further comments: _____

• Require assistance from I-CAN staff (Yes/No)

 
Displayed info for participant: Number of steps left, current steps per week, recuperation days left

--

Figure 7. Web-based pedometer compliance questions in the AERO and AERO-PA groups

**Adherence plan:** We will actively monitor adherence and compliance of exercise training using EDIN (exercise training data base) and Non-Ex PA using RED Cap™. We will review these data regularly during the intervention, and I-CAN staff meetings (bi-weekly). We will also employ several strategies to promote adherence to the study such as certificates for excellent adherence, raffles for incentive items (e.g. mug, tee-shirt), and regular adherence reports to help motivate participants. In the case of non-adherence, every ethical research-based strategy will be used to prevent participant drop-out, and continued non-adherence to the protocol. We have identified signs of poor adherence from previous training studies (i.e. lack of attendance without rescheduling, not meeting protocol goals), and have developed standardized responses by study staff. In the case of a non-adherence, a “case manager” will develop an adherence plan, and work with the participant on a one-on-one basis.

**3.10 Justification of study groups:** Similar to pharmaceutical trials, in order for the physical activity intervention used in I-CAN (AERO-PA group) to be incorporated in common practice, it must be more clinically effective compared to the current standard treatment. The current standard (or recommendation) for aerobic exercise is obtaining at least 150 minutes of moderate physical activity. Thus, the I-CAN study will determine the extent of the additional clinical benefits of increasing Non-Ex PA with aerobic exercise training.

**3.11 Statistical Considerations:** The results of the present pilot trial will be used to inform the design (effect size/statistical power) of a larger prospective intervention (to be developed into a future R01 application). Baseline participant characteristics (e.g., age sex, race, weight, BMI, waist circumference, % body fat, fat mass, lean mass, cholesterol, triglycerides, blood pressures) will be summarized by group (CON, AERO, and AERO-PA) as counts and percentages for categorical variables, and means and 95% confidence intervals or medians and IQRs for continuous variables. Adherence to protocol assessments (e.g., daily steps, minutes spent in very low activity, aerobic sessions/week, percent of peak VO2, MET levels) will be summarized similarly by week for each intervention. On study change in peak VO2, estimated METs, weight, waist circumference, cholesterol, triglycerides, and blood pressures will be summarized in an intention-to-treat analysis of (1) all participants and (2) the subset of participants who achieve a high level of adherence to protocol. Linear models will provide the primary framework for significance testing. Statistical significance of differential longitudinal changes in response to interventions will be assessed employing repeated measures mixed effects models with maximum likelihood estimation and Kenward-Rogers adjustment to the degrees of freedom in an intention-to-treat analysis of (1) and (2) for each outcome using all available data. The two interventions, measurement times (e.g., baseline, mid-intervention, study exit), race, sex and interactions will be taken as fixed effects; participants within groups will be considered as having random effects. Other covariates such as age and baseline assessments will be included in preliminary models and retained in final analytical models if warranted. The model covariance structure (e.g.: unstructured, compound symmetric, auto-regressive) across time will be investigated to enhance efficiency of statistical tests. Results for each outcome will be summarized as least squares means and 95% confidence intervals for each intervention across the assessment times (repeated measures). Model residuals will be tested to see if they have distributions that are approximately Gaussian and data transformations will be performed if needed. Group differences in baseline characteristics will be tested and corrective steps taken, such as post-stratification and adding model covariates as necessary. Linear contrasts on least squares means will be used to test differential mean changes in each outcome from baseline to subsequent assessment times between the two intervention groups. Null hypotheses will be tested against two-directional alternatives at the

nominal 0.05 significance level using Bonferroni adjusted p-values when appropriate. All statistical analyses will be performed using statistical software in SAS version 9.3.

**3.12 Limitations and Strengths:** A limitation of the project is the small sample size. However, we feel this is appropriate due to the pilot nature of the trial. In addition, the results of I-CAN will be used to determine the effect size and to power a larger randomized trial (as an R01 application) with more cardiovascular/diabetes-related outcomes. Another limitation is that we are not measuring total energy expenditure through doubly labeled water (DLW). Due to the high cost of DLW (each participant: \$750, total study costs [baseline and follow-up] = \$67,500), it is not feasible for this pilot project. However, we will incorporate DLW measurements when this study is developed into a larger randomized trial. The strengths of I-CAN are that it is a practical physical activity intervention, the core principles of which (i.e. aerobic training and attainment of high Non-Ex PA) are feasible in clinical, exercise training and public health settings. We have designed our aerobic training intervention to be consistent with public health recommendations. I-CAN will be the first training study to our knowledge with such a strong focus on the measurement of Non-Ex PA (adherence and tracking plan, pedometers [blind mode capable], and the use of internet databases to monitoring Non-Ex PA and support behavior modification) throughout the entire exercise intervention. Results of this pilot project, and the subsequent large randomized controlled trial could have implications for future public health recommendations, and other populations with co-morbid low physical activity and obesity (e.g. adults with cardiovascular disease or type 2 diabetes).

**4. Ethical aspects of the proposed research:** Ethical research practices will be strictly adhered to during the implementation of the present study, inclusive of the safety of human participants and safeguarding protected health information. The aspects of this study that carry the greatest safety risks are the exercise training and exercise testing components. All members of the investigative team are required to complete Collaborative Institutional Training Initiative (CITI), and all staff monitoring the exercise intervention and performing the exercise testing will be CPR/AED certified. The PI will oversee all aspects of this trial, and will ensure that I-CAN is implemented in an ethical manner.

Timeline of the I-CAN study	Year 1				Year 2				Year 3				Year 4			
	1	2	3	4	1	2	3	4	1	2	3	4	1	2	3	4
IRB approval, MOP development, training																
Recruitment and screening																
Baseline testing																
Follow-up testing																
Data cleaning & management																
Data analysis																

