**The Intervention Composed of Aerobic Training and Non-Exercise Physical Activity (I-CAN) study will investigate the effects of aerobic exercise training and increasing Non-EX PA on waist circumference, weight, and other cardiovascular disease risk factors in a prospective pilot trial.** We will randomize sedentary (<6,500 steps per day) obese adults (N= 45) with at least one additional cardiovascular risk factor to a: (1) structured aerobic exercise program with no intervention on Non-Ex PA (AERO group, N=15); (2) structured aerobic exercise program with the additional goal of increasing Non-EX PA (AERO-PA group, N=15), or (3) a control group (CON, N=15) for 6 months. Exercise groups will participate in the same aerobic training program (50 to 75% VO2 max), designed to be consistent with public health recommendations of 150 minutes per week of moderate physical activity. Non-Ex PA in the AERO group will be tracked throughout the entire 6 month intervention with pedometers capable of counting steps, but not displaying them to the participant (blind mode capable). The AERO-PA group will progressively increase Non-Ex PA (1,000 to 3,000 steps per day above baseline levels) throughout intervention using pedometers. The AERO-PA group will also participate in lifestyle counseling grounded in the principles of the social learning and behavioral change theories to determine/reinforce strategies to increase Non-Ex PA. The primary outcome measure will be change in waist circumference following the intervention. The study results will be used to determine the efficacy/feasibility of the intervention, and power a larger trial as an R01 application.

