#### 3.2 Approach:

The target study population of the **I-CAN** study will be sedentary obese men and women (BMI: 30-40 kg/m^2, age 40-65 yrs). We will randomize participants to aerobic training (AERO, N=15), aerobic training and increasing Non-Ex PA (AERO-PA, N=15) group or a non-exercise control group (CON, N=15) for 6 months (24 weeks). Participants in the AERO or AERO PA groups will participate in the same structured aerobic training program 3 times per week in a laboratory setting, and wear pedometers during the entire 6 month intervention (except during structured aerobic training sessions). The AERO-PA group, in addition to aerobic training, will increase Non-Ex PA progressively from 1,000 to 3,000 steps/day above baseline from week 6

[figure not shown]

Figure 3. Swift et al. *American Journal of Preventive Medicine*. 2012. Change in waist circumference in the DREW study stratified by amount of Non-Ex PA in the 4, 8 and 12KKW

to week 24 of the intervention. The CON group will continue their current physical activity habits during the intervention. **The primary outcome measure of I-CAN is the change in waist circumference following the intervention.** Secondary measures include change in fitness, body weight, body composition (fat and lean mass), pedometer determined steps/day of Non-Ex PA during the intervention, accelerometer-determined physical activity, fasting glucose, fasting insulin and homeostatic model of insulin resistance (HOMA-IR).

**3.3 Inclusion/Exclusion Criteria:** The inclusion/exclusion criteria are summarized in Table 1. The goal of the I-CAN study is to recruit adults with moderate to high CVD risk that can safely perform the supervised aerobic training in our facility. In addition, all participants must have sufficient health to increase Non-Ex PA in their daily lives, as this will not be directly supervised by study staff. Therefore, we will recruit sedentary obese men and women (age: 40-65) with elevated waist circumference (women:  $\geq 88$  cm, men:  $\geq 102$  cm), and at least one additional CVD risk factor. Individuals with type 2 diabetes and known cardiovascular disease will be excluded due to the pilot nature of this trial, and the necessity to establish the efficacy of this intervention prior its utilization in a higher risk study population.

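### Maximum likelihood in a 45-person mixed model makes standard errors about 3 to 6% too small (a 5% test runs at 5.8 to 6.5%); Kenward-Roger does not repair this, REML does

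*Combined protocol and SAP*

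**What the plan says.** Section 3.11 (Statistical Considerations) tests differential change over time with "repeated measures mixed effects models with maximum likelihood estimation and Kenward-Rogers adjustment to the degrees of freedom". The same model serves each outcome, both in all participants and in "the subset of participants who achieve a high level of adherence to protocol". Besides intervention and measurement time, "race, sex and interactions will be taken as fixed effects"; the interactions are not listed. Age and baseline values may also enter and be "retained in final analytical models if warranted". The covariance structure is left open among unstructured, compound symmetric and autoregressive. Results are least squares means with 95% confidence intervals, and tests are two-sided at 0.05, Bonferroni-adjusted where appropriate.

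The Specific Aims give the sample as "obese adults (N= 45) with at least one additional cardiovascular risk factor", 15 in each of three groups. Waist circumference, the primary outcome, is measured at three visits (section 3.4). On the use of the results, section 3.11 states: "The results of the present pilot trial will be used to inform the design (effect size/statistical power) of a larger prospective intervention". Section 3.12 repeats that "the results of I-CAN will be used to determine the effect size and to power a larger randomized trial". Neither section says which variance estimate will be carried forward.

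**The concern.** ML estimates variances as if the fixed effects were known. It takes no account of the degrees of freedom spent on estimating them, so its variance estimates are too low on average. In a large trial this is negligible. With 45 people, and fewer in the high-adherence subset, it is not.

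Naming Kenward-Roger makes the plan look protected against small-sample problems. That method allows for the uncertainty in estimated covariance parameters and sets the denominator degrees of freedom. It does not remove the downward bias that ML puts into those parameters.

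Three things are at stake: the confidence interval and test for the primary waist contrast, the same quantities for every secondary outcome, and any model-based variance used to power the later trial.

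**Working it through.** The documents give no standard deviation, effect size, dropout rate or power figure, so there is no plan figure to reproduce beyond 3 × 15 = 45.

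**Inputs.** n = 45, three groups, three visits, ML with Kenward-Roger, two-sided 0.05 (all from the plan). The number p depends on what the unlisted interactions are:

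- Only group crossed with time: p = 3, whether race and sex are main effects or absent.
- Race and sex also crossed with time: p = 5, if race has two levels (assumed).

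**Standard error, complete data.** SE(ML) / SE(REML) = √((n − p)/n).

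- p = 3: √(42/45) = 0.966, so the SE is 3.4% too small; variance low by 3/45 = 6.7%.
- p = 5: √(40/45) = 0.943, so the SE is 5.7% too small; variance low by 5/45 = 11.1%.

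**True size of the 5% test.** Size = 2·P(t on n − p df > t_crit·√((n − p)/n)). The critical value is taken on n − p df, or on n df, which is what Kenward-Roger returns from an ML fit with complete data under an unstructured covariance.

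- p = 3: 2.018 × 0.966 = 1.950 gives 5.8%; with 45 df, 2.014 × 0.966 = 1.946 also gives 5.8%.
- p = 5: 2.021 × 0.943 = 1.906 gives 6.4%; with 45 df, 2.014 × 0.943 = 1.899 gives 6.5%.

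Compound symmetry, with 2(n − p) and 2n df, gives the same SE ratios and sizes. In 200,000 simulated complete-data trials, ML with 45 df rejected in 5.8% (p = 3) and 6.5% (p = 5); REML rejected in 5.0% and 5.1%.

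**What Kenward-Roger does.** Computed on ML fits with an unstructured covariance, it changes the SE of the week-24 contrast by 0.0% with complete data and by 0.3 to 0.7% with 10 to 20% dropout. The simulation below used 4,000 null trials per row (Monte Carlo error about 0.35 to 0.4 points). Dropout rates are assumed, with half the dropout before and half after week 12. SAS 9.3 itself was not run.

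| Model | Dropout | SE ratio ML/REML | Size, ML + KR | Size, REML + KR |
|---|---|---|---|---|
| Race and sex as main effects | 0% | 0.966 | 5.7% | 4.9% |
| Race and sex as main effects | 10% | 0.963 | 5.5% | 4.8% |
| Race and sex as main effects | 20% | 0.958 | 6.5% | 5.3% |
| Race and sex crossed with time (p = 5) | 0% | 0.943 | 7.1% (exact 6.5%) | 5.6% (exact 5.0%) |
| Race and sex crossed with time (p = 5) | 10% | 0.937 | 6.7% | 5.2% |
| Race and sex crossed with time (p = 5) | 20% | 0.930 | 6.8% | 5.3% |

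**Other readings, same formula.**

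- Control group left out of the model (n = 30, p = 2 or 4): SE 3.4% or 6.9% too small, size 5.8% or 6.7 to 6.8%.
- High-adherence subset, size not stated; at an assumed 36 or 30 people: SE 4.3% or 5.1% too small (p = 3), 7.2% or 8.7% (p = 5); sizes 6.0 to 7.4%.
- Upper bound, a full group × race × sex × time model (p = 12): SE 14.4% too small, size about 9%. The plan does not state this model.

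**Later trial.** If the ML variance is used to size it for 80% power, true power is Φ((1.960 + 0.842)·√(1 − p/45) − 1.960), other inputs fixed.

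- p = 3: 2.802 × 0.966 − 1.960 = 0.747, power 77%.
- p = 5: 2.802 × 0.943 − 1.960 = 0.681, power 75%.

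For scale, an unbiased REML variance on 42 df varies enough by chance to put true power anywhere from about 60% to 92% (95% range).

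**The case against.** The strongest reply is that the effect is minor. On the reading that adds least to the text (p = 3), the excess error is 0.8 points and the SE shift 3.4%. The chance variation of an SE estimated on 42 df is about 1/√(2 × 42) = 11%. The trial is a pilot and names its small sample as a limitation. This stands as a statement of size. It does not make the bias harmless, because chance error goes both ways and this goes one way.

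The plan may also use maximum likelihood loosely to mean REML. That is possible, and naming REML would then only confirm the intent. As written, the text says ML, and an analyst following it would fit ML.

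Bonferroni adjustment could mask some of the excess. If the week-12 and week-24 contrasts were adjusted together (assumed correlation 0.5 to 0.85), familywise error under ML would be about 4.7 to 5.6% at p = 3 and 5.3 to 6.4% at p = 5. But the plan does not say when it adjusts, and the adjustment leaves the SE itself uncorrected.

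Two limits remain. REML restores the nominal size for a model fixed in advance; selecting the covariance structure and covariates from the data is a separate matter and was not simulated. The autoregressive structure was not checked. And the loss of power in a later trial applies only if a model-based ML variance is carried forward.

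**Conclusion.** The concern holds. Followed as written, section 3.11 gives standard errors 3.4% (p = 3) to 5.7% (p = 5) too small with complete data, and tests of true size 5.8 to 6.5% at a nominal 5%. Dropout and the smaller high-adherence subset enlarge the shortfall. With complete data the treatment estimates do not change; only standard errors, intervals, p-values and variances do. The complete-data ratios are exact given p. The range rests on which interactions are fitted and on two race levels; the dropout and subset figures rest on assumed rates and sizes. This is a modest but systematic error that should be fixed.

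**What to change.** In section 3.11, state that all reported estimates, confidence intervals and tests come from REML fits with Kenward-Roger. Reserve ML for likelihood comparisons between models with different fixed effects, such as deciding which covariates to retain. If a model-based variance is passed to the larger trial, specify the REML one. The interaction terms need no change to cure this bias.

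The cost is one software option and one sentence. With complete data, standard errors rise by 1/0.966 − 1 = 3.5% (p = 3) to 1/0.943 − 1 = 6.1% (p = 5), which removes the shortfall. If covariates are chosen by likelihood comparison, the chosen model is fitted once by ML for the choice and once by REML for the report.
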